#### **9.2.5. Day 15 ( $\pm$ 4 days)**

- Physical examination
- Performance Status
- Vital signs (blood pressure, heart rate, respiratory rate, temperature)
- Chemistries (electrolytes, creatinine, BUN, magnesium, phosphorus)
- CBC
- Assessment for adverse events
- Assessment for concomitant medications
- Blood sample for panitumumab-IRDye800 antibody and Zr-panitumumab antibody and immunogenicity
- ECG

#### **9.2.6 Day 30 ( $\pm$ 4 days)**

- Investigator or study staff will contact the subject by telephone or review of electronic medical record data to collect any additional adverse events that are attributable to the study and/or concomitant medications.

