TREATMENT SCHEDULE	
Subjects will undergo surgical resection at 2-5 days after infusion (see figure below) based on expected half-life of panitumumab-IRDye800. Imaging will be performed intraoperatively using the optical imaging devices listed in Appendix B and the <math>^{89}\text{Zr}</math>-detecting/imaging devices listed in Appendix C. The oncologic surgery will be conducted following the standard of care. Ex vivo imaging of the specimen prior to pathological assessment will be performed using non-invasive radioactive and fluorescence imaging modalities that do not violate or destroy the tissue.
  
IV infusion panitumumab-IRDye800 and <math>^{89}\text{Zr}</math>-panitumumab
 
<math>^{89}\text{Zr}</math>-panitumumab PET/CT imaging*
 
Surgery
 
Follow-up**
 
Cohort 1 (n=7: LN-)
 
Cohort 2 (n=7): LN+
 
Day 0
 
Day 0 - Day before surgery
 
Day 2-5
 
Day 15
 
Day 30
 
*Patients (n=3-5) in de dosimetry substudy will receive 3 PET/CT scans between day 0 and day of surgery. **On day 15 patients will come to the clinic. At day 30 patients will be called.

PRIMARY OBJECTIVE(S)	
Determine the sensitivity and specificity of <math>^{89}\text{Zr}</math>-panitumumab for the detection of tumor-involved regional lymph nodes.
 
As defined by histological and/or pathological evaluation (gold standard), the total number of tumor-positive nodes will be determined and correlated to the radiologically-suspicious nodes identified by <math>^{89}\text{Zr}</math>-panitumumab and <math>^{18}\text{F}</math>-FDG contrast agents using PET/CT and/or PET/MRI imaging. The specificity and sensitivity of <math>^{89}\text{Zr}</math>-panitumumab will be calculated and compared to the specificity and sensitivity of <math>^{18}\text{F}</math>-FDG for metastatic lymph node identification.

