SAMPLE SIZE AND DURATION OF STUDY	
It is anticipated that 14 subjects will be enrolled into the study. Safety data and adverse events will be reported at 15 days after the last subject receives the infusion, which is in excess of 4-fold the half-life of the largest dose of pantumumab-IRDye800 (2.3 days) and of the half-life of Zr-panitumumab (3.3 days). Each subject will be followed for 30 days following the last dose of study medication.
 
It is anticipated that the study will require 12 to 18 months to be completed.

STATISTICAL CONSIDERATIONS	
General analysis tools All specimens from both cohorts will be pooled for the primary and secondary analyses. We will use the matched pair Durkalski's test that accounts for the correlation of multiple specimens per patient, to compare the specificity and sensitivity of Zr-panitumumab-PET to F-FDG-PET. We will compare the odds of a false negative with Zr-panitumumab-PET relative to the odds of obtaining a false negative with F-FDG-PET.
 
Approach to drawing statistical inference Significance for all tests will be assessed at the 0.05 level and 95% confidence intervals will be reported and interpreted.
 
Descriptive statistics We will present means and standard deviations (or medians and interquartile ranges when appropriate) for continuous characteristics such as maximum standard uptake values (<math>SUV_{max}</math>) as determined with Zr-panitumumab-PET and F-FDG-PET and radioactivity counts of Zr-panitumumab in the node(s) as determined with the PET probe, and tumor-to-background ratios (TBRs) and mean fluorescence intensity (MFI) for panitumumab-Irdye800. For categorical variables such as drainage pattern and number of lymph nodes visualized, we will present frequency statistics. Graphical tools such as heat maps, histograms, and boxplots will be used to assess distributional properties of continuous variables. We will illustrate the nature of the relationship between <math>SUV_{max}</math>/radioactivity counts and/or MFI/TBRs and/or drainage pattern across all subjects, the relationship will be illustrated with a heat map and spaghetti plot. When appropriate, transformations – including a log-based transformation – may be considered to stabilize variance.

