**Outcome measures to answer the primary and secondary objectives set:**

Preoperative data:

1. Collect safety data on tracer-infusion.
2. The number and location of F-FDG-PET positive nodes.
3. The number and location of Zr-panitumumab-PET positive nodes.

Intraoperative data:

4. The number and location of Zr-panitumumab-PET positive nodes.
5. The number and location of panitumumab-IRDye800 positive nodes.

Post-operative data:

6. Collect safety data in follow-up (up to 30 days post-infusion).
  - a. This includes tests and observations to identify both acute and late-treatment specific toxicity: vital signs; physical exam; toxicity grading; assignment of performance status; hematology; and blood chemistries (basic metabolic profile to include magnesium and phosphorus). NCI Common Toxicity Criteria v5.0 will be used for grading of toxicity.
7. Determine *ex vivo* fluorescence imaging information on panitumumab-IRDye800 (method described previously in (21)).
8. Determine the histo-pathological status of the primary tumor.
9. Determine the histo-pathological status of the lymph nodes: tumor-positive (isolated tumor cells, micro- or macro-metastasis) or tumor-negative.
10. Determine, using immunohistochemistry, on the surgically excised tissue specimens:
  - a. Tumor tissue viability
  - b. EGFR expression
  - c. Vessel density

We have previously described the methods for analysis in (26).

For qualification and quantification of the fluorescence signal and the radioactive signal, we follow the following rules:

- *Intraoperative fluorescence assessment of panitumumab-IRDye800:*

There will be no set level of fluorescence whereby we consider tissue positive or negative; it is based on operator's impression.

- *Ex vivo fluorescence assessment of panitumumab-IRDye800:*

From the fluorescence images taken in the operation room, we will calculate tumor-to-background ratios (TBRs) as such to define a more quantitative read-out (similar to as described in the IRB-35064 study). Based on the current data available from our IRB-35064, in our 50 mg cohort, we found an average TBR of  $6.53 \pm 1.2$ , a sensitivity of  $89 \pm 5.1\%$ , a specificity of  $92 \pm 3.5\%$  (AUC:  $0.93 \pm 0.05$ ). The NPV and PPV were  $94 \pm 2.8\%$  and  $92 \pm 9.5\%$ , respectively. We will extrapolate these findings to the current study to further validate the findings from our phase I study (IRB-35064).

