#### **4.8 Alternatives and Risk Protection / Mitigation**

Alternatives

- This study is in the setting of tumor excision of biopsy-confirmed diagnosis of HNSCC, and the experimental component is infusion of  $^{89}\text{Zr}$ -panitumumab and panitumumab-IRDye800, which may help visualize the tumor and tumor margins as well as identify tumor-loaded lymph nodes for the surgeon. The surgery itself is considered regular medical care. Therefore, the alternative to participating in this study is to have the tumor excision surgery without the  $^{89}\text{Zr}$ -panitumumab and panitumumab-IRDye800 infusion.

Procedures to protect against and minimize potential risks:

- This study is designed to enroll appropriate subject populations (see Section 3.1 Inclusion Criteria, and Section 3.2 Exclusion Criteria).

- Subjects will be monitored regularly by the investigators and the study team after investigational  $^{89}\text{Zr}$ -panitumumab and panitumumab-IRDye800 and surgery, through 30 days ( $\pm 1$  week) post- $^{89}\text{Zr}$ -panitumumab and panitumumab-IRDye800 treatment, for adverse events by means of physical exams, blood tests, and ECGs.
- Subjects will be given a 24-hour emergency number in case problems arise between clinic visits.
- Subject records will be kept in a secure location at Stanford University Medical Center accessible only to authorized personnel.

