## **7.5 Safety Monitoring and Reporting**

### **7.5.1 Monitoring of Adverse Events**

Both serious and non-serious adverse events (AEs) will be clearly noted in source documentation and listed on study specific Case Report Forms (CRFs). The Protocol Director (PD) or designee will assess each AE to determine whether it is unexpected according to the Informed Consent, Protocol Document, package insert, or cross-referenced Investigator's Brochure, and related to the investigation.

All adverse events (AEs), regardless of seriousness or relationship to study drug, are to be collected only on designated study dates from signing of informed consent through 30 days after administration of study drug, and recorded in the study specific worksheets, with the following exceptions:

- AEs that are solely laboratory values; are not related to the study drug; AND are clinically non-significant may not be collected.
- Non serious AEs that are not related to the study drug; are not clinically significant; AND are expected in the post-surgery clinical setting may not be collected.
- SAEs that occur from signing of informed consent to prior to administration of study agent may not be collected unless assessed as possibly, probably or definitely-related to a study procedure.

All patients enrolled in this study receive surgical intervention in the course of their standard of care. As a consequence of this surgery, patients may experience certain expected and normal adverse events. The following post-operative adverse events will be captured only in the patient's Electronic Health Record (EHR) source documentation and not in the adverse event log. If the adverse event exceeds the grading listed below or occurs outside the post-operative time window, the adverse event will be recorded in the Adverse Event Logs.

- Surgical wound site and associated, expected secondary signs and symptoms, including:
  - CTCAE v5.0 Grade 1 erythema, edema, and pruritis.
  - CTCAE v5.0 Grade 1 pain associated with surgical wound, including headaches – mild pain, little to no limit on adult daily life.
  - CTCAE v5.0 Grade 1 nausea, vomiting, and dysphagia.
  - CTCAE v5.0 Grade 1 weight loss, anemia, and electrolyte abnormalities.
  - CTCAE v5.0 Grade 2 trismus.

Whenever possible, symptoms should be grouped as single syndrome or diagnosis. The Investigator should specify the date of onset, maximal intensity, corrective therapy given, outcome, and his/her assessment of causality.

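### The Day 30 close-out is described inconsistently in mode, window and scope of events, so a compliant record review on Day 26 can end adverse-event collection 4 days short of the stated 30

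*Combined protocol and SAP*

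**What the plan says.** Three passages commit the study to 30 days of safety follow-up. The synopsis states "Each subject will be followed for 30 days following the last dose of study medication". The outcome-measure list in Section 2.4 includes "Collect safety data in follow-up (up to 30 days post-infusion". Section 7.5.1 says that adverse events, whatever their seriousness or causal relation and apart from listed exceptions, "are to be collected only on designated study dates from signing of informed consent through 30 days after administration of study drug".

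The last of those dates is then described in different ways:

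- The note to the synopsis figure: "At day 30 patients will be called".
- Section 9.2.6, headed Day 30 ±4 days: staff will "contact the subject by telephone or review of electronic medical record data to collect any additional adverse events", limited to events attributed to the study. The sentence also mentions concomitant medications. Whether these are a second possible cause or a second item to collect is unclear, but on either reading only attributed events are sought.
- Table 5 in Section 9.1: Day 30 ±4 days, with only adverse events and concurrent medications marked. Its footnote sends the reader to Section 7.5.1 for how events are monitored.
- Section 4.8: monitoring "through 30 days ( $\pm 1$ week") after dosing, "for adverse events by means of physical exams, blood tests, and ECGs".

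**The concern.** Section 7.5.1 ties collection to designated dates, and Day 30 is the last one in Table 5. How and when that contact is made therefore decides whether the final part of the 30 days is observed at all. A contact before Day 30 cannot report what has not yet happened. A record review finds only what reached the record being read, whereas Section 7.5.2 stresses that subjects should report new or worsening symptoms. Both gaps can only lose events; neither can add any. Two subjects with the same experience could end with different entries because one was telephoned on Day 32 and the other had a chart read on Day 26. At stake is the completeness of late safety data in a study that Section 2.3 describes as first-in-human for this combination of agents.

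**Working it through.** The plan gives no figure to reproduce. The check sets the passages side by side and does the window arithmetic.

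**Step 1. The passages compared.**

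| Place | Mode | Timing | Events sought |
|---|---|---|---|
| Synopsis figure note | telephone call | Day 30, no tolerance given | not stated |
| Section 9.2.6 | telephone or record review | ±4 days | attributed events only |
| Table 5 | not stated | ±4 days | refers to Section 7.5.1 |
| Section 4.8 | examinations, blood tests, ECGs | ±1 week | adverse events |
| Section 7.5.1 | designated dates only | through 30 days | all, with listed exceptions |

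Mode differs three ways: call, call or record review, and in-person procedures. Timing differs between Section 4.8 and the schedule. Scope differs between Sections 9.2.6 and 7.5.1. The procedures named in Section 4.8 have no Day 30 entry in Table 5; the last scheduled physical examination, blood tests and ECG are at Day 15.

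**Step 2. Earliest compliant close-out.** Section 9.1 says enrolled subjects follow the schedule in Table 5, and Section 9.2.6 gives the same window. Earliest day: 30 − 4 = Day 26. Latest day: 30 + 4 = Day 34.

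**Step 3. What a Day 26 contact leaves out.** Days 27 to 30: 30 − 26 = 4 days, and 4/30 = 13%. No later designated date exists to collect them. A contact on Day 30 to 34 leaves out none.

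**Step 4. When the subject was last asked if Day 30 is record review alone.** The preceding scheduled assessment is Day 15 ±4 days: 15 − 4 = Day 11 to 15 + 4 = Day 19. The days about which the study has not asked the subject then number between 30 − 19 = 11 and 30 − 11 = 19 of the 30. With a review on Day 26, the days up to Day 26 are covered by the record only, and Days 27 to 30 by nothing scheduled.

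**The case against.** A ± window around a nominal visit day is ordinary scheduling, and this one is symmetric, so many contacts may fall on or after Day 30 and lose nothing. That is fair; the point is that the earlier contacts also comply.

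The safety assessment does not hinge on Day 30. Section 4.3 chooses Day 15 as the time point to assess safety and does not expect panitumumab-IRDye800 to be detectable beyond 12 days. Section 5.2.2 expects mainly infusion or allergic reactions. The synopsis reports safety 15 days after the last infusion. The outcomes in Section 10 are nodal, and Section 12 contains no adverse-event analysis. All of this stands and keeps the point small.

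Other routes exist. Section 7.5.2 requires serious events to be reported within 24 hours of knowledge and tells subjects to report symptoms throughout participation; Section 4.8 gives them an emergency number. For serious events this largely answers the point. For non-serious events it helps less, because it depends on the subject volunteering the symptom and sits uneasily with collection on designated dates only.

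A reader might go further and infer from Section 4.8 that the count can close on Day 23 without the subject being asked. The documents do not support that. The ±1 week appears only in a general risk-mitigation bullet that describes in-person monitoring, while record review appears only in Section 9.2.6, where the earliest day is 26. No passage joins the two. Nor do the documents support an estimate of the share of late events missed, because they give no late event rate.

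**Conclusion.** The inconsistency is real and minor. As written, a record review on Day 26 meets Section 9.2.6 and Table 5, yet leaves 4 of the 30 days (13%) promised in Section 7.5.1 with no later collection date, and the subject may last have been asked by the study on Day 11 to 19. The consequence is possible under-capture of late, mainly non-serious adverse events, in one direction only. No primary or secondary outcome and no stated adverse-event rate is affected.

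The 13% is the edge of the allowed window, not an expected loss. It assumes that days are counted from dosing on Day 0, that contact is made on the earliest allowed day, and that nothing is picked up later. The further point about asking the subject assumes that record review replaces the call. How often either would happen cannot be read from the documents.

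**What to change.** Reconcile the synopsis note, Section 4.8, Section 7.5.1, Table 5 and Section 9.2.6 to one Day 30 data-collection rule:

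- **Mode:** the telephone contact already promised in the synopsis, with record review as a supplement. Record review alone serves only when the subject cannot be reached, and is flagged as such in the case report form.
- **Timing:** on or after Day 30, for example Day 30 to 34, with questions covering the whole time since the previous assessment.
- **Scope:** the same events as Section 7.5.1, with its listed exceptions, so that attribution is judged after collection and does not act as a filter on it.

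Section 4.8 must also be brought into line with Table 5 on its window and on the procedures it names. Which monitoring is clinically wanted is for the investigators to settle.

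The cost is wording in five places, at most 14 short calls (one per subject) and a slightly narrower contact window. Sample size and analysis are unchanged.

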### **9.3 Description of Evaluations / Procedures**

#### **9.3.1 *Laboratory Evaluations***

Blood specimens will be collected for hematology (WBC, RBC; hemoglobin, hematocrit, and platelet counts), basic metabolic profile electrolytes, creatinine, BUN, magnesium and phosphorus, and serum pregnancy if necessary. If laboratory evaluations are obtained within 21 days of Day 0, they do not have

to be repeated. Blood will be collected for fluorescent-labeled antibody pharmacokinetics and furthermore, blood will be obtained and banked for future analysis of immunogenicity against the study drug as requested by the FDA in pre-IND conversations.

### **9.3.2 Physical Examinations**

A physical examination will be conducted to include review of all major systems prior to enrollment to study. If the initial physical examination is obtained within 21 days of Day 0, the exam does not have to be repeated. Standard head and neck examination and system-oriented physical examination will be conducted on other visits.

### **9.3.3 Medical History**

A complete medical history including age, sex, race, current medications, any current or previous medical conditions, any previous surgeries, smoking history, and alcohol use will be done at screening.

### **9.3.4 Vital Signs**

Vital signs including blood pressure, heart rate, respiratory rate, and temperature will be collected at each clinic visit. Height and weight will be collected at screening.

### **9.3.5 Tumor and lymph node imaging**

Imaging will be done utilizing the optical imaging devices (see Appendix B for details). The camera head will be placed over the tumor and/or lymph nodes and images will be obtained and recorded.

### **9.3.6 Cardiac Monitoring**

Preclinical studies performed at UAB (2013) identified a small, but statistically significant increase in QT-intervals using cetuximab. These studies in non-human primates after administration of cetuximab-IRDye800 identified an increase in the QTc interval for cetuximab alone compared to cetuximab-IRDye800. There was also a statistically significant difference between the QTc interval between the cetuximab and cetuximab-IRDye800 that will require assessment of interval ECG and exclusion criteria of patients at risk for arrhythmias, see exclusion criteria. Screening ECG and intermittent ECG data will be obtained as part of the study. We reference the full toxicology report for Cetuximab-IRDye800 (IND 115706) recently submitted to the FDA. However, more recent investigation (40) has failed to substantiate this QTc risk in panitumumab-IRDye800 and has further shown no significant evidence of cardiac toxicity.

An ECG will be obtained during the screening period, on day of infusion (at 30 min ( $\pm$ 10) after the end of panitumumab-IRDye800 infusion and at the end of the 1 hour observation period after completion of injection of  $^{89}\text{Zr}$ -panitumumab) and on Day 15. A previous ECG that was obtained as part of standard of care may be used as the baseline ECG if obtained within 21 days prior to injection and will be reviewed any time prior to eligibility. QT/QTc interval will be assessed for each time point. A supervising physician will review the ECG results the same day they are recorded, the final review can be delayed (pending on availability of final reading) but initial review for safety is done the same day.

## **10. MEASUREMENTS**

### **10.1 Primary Outcome Measure**

**The number (proportion) of lymph nodes determined to be tumor-positive by histological and/or pathological evaluation that were predicted to be tumor-positive by  $^{89}\text{Zr}$ -panitumumab labeling.**

We will compare the number and location of  $^{18}\text{F}$ -FDG-avid nodes within the regional lymphatics to the number and location of  $^{89}\text{Zr}$ -panitumumab-avid nodes in relation to the postoperative neck dissection histopathology (gold standard).

**Outcome Measure:** Preoperatively, the location and number of  $^{18}\text{F}$ -FDG-avid nodes as well as the number and location of  $^{89}\text{Zr}$ -panitumumab-avid nodes will be determined by 2 board-certified Nuclear Medicine physicians ([name] and [name]). Once all radioactive and fluorescent nodes are removed intraoperatively, standard of care will be

performed via completion neck dissection. The excised tissue specimens will be sent to pathology where the tumor status of the lymph nodes will be determined (histology serves as our gold standard). This will allow us to determine true and false positive and negative tumor values for Zr-panitumumab and F-FDG in identifying the tumor-loaded lymph nodes.

**Time Frame:** Final false positive and negative rate, sensitivity and specificity of sentinel node detection using Zr-panitumumab can be determined towards the completion of the trials (once all subjects have been included and all the data has been collected).

**Safety Issue:** No

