TREATMENT SCHEDULE	
Subjects receive F-FDG-PET/CT and/or F-FDG-PET/MRI as part of their standard of care prior to study enrollment. After infusion of study agents on Day 0, subjects will undergo Zr-panitumumab PET/CT imaging between Day 0 and the Day before Surgery. Subjects enrolled in the dosimetry sub-study will undergo imaging on day 0 to the day before surgery, for a total of 3 PET/CT scans.
 
Subjects will undergo surgical resection at 2-5 days after infusion (see figure below) based on expected half-life of panitumumab-IRDye800. Imaging will be performed intraoperatively using the optical imaging devices listed in Appendix B and the Zr-detecting/imaging devices listed in Appendix C. The oncologic surgery will be conducted following the standard of care. Ex vivo imaging of the specimen prior to pathological assessment will be performed using non-invasive radioactive and fluorescence imaging modalities that do not violate or destroy the tissue.
														
TREATMENT SCHEDULE	Subjects receive  F-FDG-PET/CT and/or  F-FDG-PET/MRI as part of their standard of care prior to study enrollment. After infusion of study agents on Day 0, subjects will undergo  Zr-panitumumab PET/CT imaging between Day 0 and the Day before Surgery. Subjects enrolled in the dosimetry sub-study will undergo imaging on day 0 to the day before surgery, for a total of 3 PET/CT scans.														

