For an overview of the proposed study, see Study Schema (page 9), and the dosing schedule below. Briefly, subjects will undergo F-FDG-PET prior to study enrollment, as is standard of care. Administration of panitumumab-IRDye800 will occur by IV over 15 minutes, followed by a 30-minute observation period. Administration of Zr-panitumumab will occur by IV, per radioactive drugs administration policies. The subjects will be observed for 1 hour following the Zr-panitumumab injection.

After infusion of study agents on Day 0, subjects will undergo Zr-panitumumab PET/CT imaging. One scan will be performed at any time starting on Day 0 (after end of observation period post Zr-panitumumab administration) and until the day before surgery (inclusive). Subjects enrolled in the dosimetry sub-study will undergo three scans, performed at any time starting on Day 0 (after end of observation period post Zr-panitumumab administration) and until the day before surgery. If available, the scans will be performed on Day 0, Day 1 and on the day before surgery.

Subjects will undergo surgical resection 2-5 days after infusion of study drugs. Imaging will be performed intraoperatively using a novel beta probe and/or high-energy gamma probe (see Appendix C for a list of devices) and the optical imaging devices (see Appendix B for a list of devices), to assess the tumor and lymph node(s) prior to resection, and the wound bed after surgical removal. The surgery will be conducted in the standard of care, and the surgeon will not use the imaging data to make decisions.

*Ex vivo*, imaging of the specimens prior to pathological assessment will be performed using non-invasive imaging modalities that do not violate or destroy the tissue. These may include beta probe and/or high-energy gamma probe, an open-field imaging system, a closed-field imaging system and a fluorescence flatbed scanning device (see Appendix B and C for a list of devices). Additionally, a closed Cherenkov imaging system may be used to image the specimen after removal (see Appendix C). Methods have been described in detail in the literature (20-25).

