## **3. PARTICIPANT SELECTION AND ENROLLMENT PROCEDURES**

### **3.1 Inclusion Criteria**

1. Biopsy-confirmed diagnosis of squamous cell carcinoma of the head and neck.
2. Subjects diagnosed with any T stage, any subsite within the head and neck that are scheduled to undergo surgical resection. Subjects with recurrent disease or a new primary will be allowed.
3. Planned standard of care surgery with curative intent for squamous cell carcinoma.
4. Age  $\geq$  19 years.

5. Have acceptable hematologic status, coagulation status, kidney function, and liver function including the following clinical results:

Hemoglobin  $\geq$  9 gm/dL  
White blood cell count  $>$  3000/mm^3  
Platelet count  $\geq$  100,000/mm^3  
Serum creatinine  $\leq$  1.5 times upper reference range

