## 10.2 Secondary Outcome Measures

**The number (proportion) of lymph nodes determined to be tumor-positive by histological and/or pathological evaluation that were NOT predicted tumor-positive by Zr-panitumumab labeling.**

We will compare the number and location of F-FDG-avid nodes within the regional lymphatics to the number and location of Zr-panitumumab-avid nodes in relation to the postoperative neck dissection histopathology (gold standard).

**Outcome Measure:** Preoperatively, the location and number of F-FDG-avid nodes as well as the number and location of Zr-panitumumab-avid nodes will be determined. Once all radioactive and fluorescent nodes are removed intraoperatively, standard of care will be performed via completion neck dissection. The excised tissue specimens will be sent to pathology where the tumor status of the lymph nodes will be determined (histology serves as our gold standard). This will allow us to determine true and false positive and negative tumor values for Zr-panitumumab and F-FDG in identifying the tumor-loaded lymph nodes. Specifically we will look for lymph nodes that were F-FDG positive on preoperative imaging and/or fluorescently labeled by panitumumab-IRDye800, but do not show uptake of Zr-panitumumab.

**Time Frame:** Final false positive and negative rate, sensitivity and specificity of sentinel node detection using panitumumab-IRDye800 can be determined towards the completion of the trial (once all subjects have been included and all the data have been collected).

**Safety Issue:** No

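### Section 2.4 and Sections 10.1/10.2 contradict each other on whether tracer signal guides node removal; the second wording leaves room for selective verification outside the dissection field and a small bias toward 89Zr

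*Combined protocol and SAP*

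**What the plan says.** Two accounts of the surgery stand in the current text.

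- Section 2.4: "The surgery will be conducted in the standard of care, and the surgeon will not use the imaging data to make decisions". The synopsis agrees: "The oncologic surgery will be conducted following the standard of care".
- Section 10.1, under the primary outcome, begins the sequence with "Once all radioactive and fluorescent nodes are removed intraoperatively, standard of care will be". Section 10.2 gives the whole sentence: "Once all radioactive and fluorescent nodes are removed intraoperatively, standard of care will be performed via completion neck dissection".

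Three other statements bear on the consequence. The probe and optical readings are available before removal, because Section 2.4 has them used "to assess the tumor and lymph node(s) prior to resection, and the wound bed after surgical removal". The reference standard covers only what is taken out: "The excised tissue specimens will be sent to pathology where the tumor status of the lymph nodes will be determined". Eligibility does not fix the extent of neck dissection; Section 3.1 asks for "Planned standard of care surgery with curative intent for squamous cell carcinoma".

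The synopsis and Section 12 pool both cohorts for the primary and secondary analyses. Neither says whether a node must lie in the planned dissection field to be counted, and no CRF item is described that would identify a node from outside it.

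**The concern.** Under Section 2.4, which nodes reach pathology does not depend on the tracer. Under Sections 10.1 and 10.2, a radioactive or fluorescent signal is itself a reason for removal, and the standard dissection comes afterwards. For a node outside the standard field, the result of the index test (or of the fluorescent agent built on the same antibody) can then decide whether the node receives the reference standard. This is verification driven by the index test.

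The primary comparison of 89Zr-PET with FDG-PET would be exposed. Metastatic nodes outside the field would enter the table mainly when 89Zr-positive, while metastases there that both panitumumab agents missed would stay unseen. FDG-avid nodes are not named as a trigger for removal. The secondary objective (odds of a false negative, and NPV) uses the same table. If nodes are not marked as inside or outside the field at surgery, they cannot be separated reliably later.

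**Working it through.** **The plan's own figures (Section 12).** 14 subjects × 30 nodes = 420. With an ICC of 0.005, the effective sample size is 420/(1 + 29 × 0.005) = 366.8, matching the stated 367. At 7.5% prevalence this is 367 × 0.075 = 27.5 effective tumor-positive nodes, or 420 × 0.075 = 31.5 by raw count. An exact one-sided McNemar test with n = 27, p10 = 0.275 and p01 = 0.025 gives power 0.714, matching the stated 71%. The point made here does not dispute that figure; the calculation only sizes the set of positive nodes.

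**Inputs for the bias.**
- n = 31.5 metastatic nodes in the field, all verified.
- S = 0.70, the plan's lower sensitivity, assumed true for both tests.
- Discordance 0.3, the plan's figure. With equal sensitivities this means p10 = p01 = 0.15 and both-positive = 0.70 − 0.15 = 0.55.
- m = metastatic nodes outside the field across the trial. **The documents give no figure; 2 to 6 is an assumption.**

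**Upper case: every 89Zr-PET-positive out-of-field metastasis is removed, and no PET-negative one.**

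89Zr = (22.05 + 0.70m)/(31.5 + 0.70m)

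FDG = (22.05 + 0.55m)/(31.5 + 0.70m)

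| m | 89Zr | FDG | False advantage |
|---|---|---|---|
| 2 | 23.45/32.9 = 0.713 | 23.15/32.9 = 0.704 | 0.9 points |
| 4 | 24.85/34.3 = 0.724 | 24.25/34.3 = 0.707 | 1.7 points |
| 6 | 26.25/35.7 = 0.735 | 25.35/35.7 = 0.710 | 2.5 points |

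With 27.5 in place of 31.5 and 1 to 5 nodes outside, the false advantage is 0.5 to 2.4 points. Where the true difference is the plan's 0.25, it would read as 0.251 to 0.256.

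**Fluorescence also triggers removal.** Suppose (assumption) that 90% of out-of-field metastases are removed, including all PET-positive ones, so 0.20m are PET-negative. Then 89Zr = (22.05 + 0.70m)/(31.5 + 0.90m), which is 23.45/33.3 = 0.704 at m = 2 and 26.25/36.9 = 0.711 at m = 6. If removal of the PET-negative nodes does not depend on FDG status, half of them are FDG-positive (0.15/0.30), so FDG = (22.05 + 0.65m)/(31.5 + 0.90m). The false advantage is then 0.05m/(31.5 + 0.90m), or 0.3 to 0.8 points.

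**Specificity.** The plan implies 420 − 31.5 = 388.5 benign nodes. At its lower specificity of 0.70, 271.95 are true negatives. Adding 2 to 6 benign 89Zr-positive nodes from outside the field (assumption) gives 271.95/390.5 = 0.696 to 271.95/394.5 = 0.689, a loss of 0.4 to 1.1 points for 89Zr.

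**Inside the field.** Completion dissection sends tracer-negative nodes to pathology too. Removing the tracer-positive ones first changes the order, not the verification, and the excess is zero.

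**The case against.** The strongest reply is that few or no such nodes may exist. Section 2.1 gives complete lymphadenectomy as the standard of care in this setting, the objectives concern regional nodes, and Section 10.1 compares avid nodes in the regional lymphatics with neck dissection histology. No section says that nodes outside the dissection will be taken. This stands as a reason to expect a small number. It does not make the number zero: extent of dissection is not fixed, Section 3.2 excludes only previous bilateral neck dissection, and the background discusses rerouting and skip metastases.

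Two stronger readings are tempting, and the documents support neither.

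- A reader might infer that out-of-field nodes can add 89Zr true positives but never false negatives. The 89Zr result in the primary outcome is the preoperative PET/CT read, whereas the removal trigger is intraoperative radioactivity or fluorescence. Section 2.4 provides for tissue that is fluorescent only, and Section 10.2 sets out to look for fluorescent nodes without 89Zr uptake. Such a metastasis, removed from outside the field, counts as an 89Zr false negative. The plan expects the two labels to agree, so the offset is partial.
- A reader might infer that FDG gains nothing and stays at 0.70, which would give a false advantage of 1.3 to 3.5 points for m = 2 to 6. This needs the tests to be independent given disease, and independence at 0.70 and 0.70 implies discordance of 2 × 0.70 × 0.30 = 0.42. The plan assumes 0.3, under which FDG is enriched too.

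A last objection is materiality. With 31.5 positive nodes at 0.70, the 95% half-width before any allowance for clustering is 1.96 × √(0.21/31.5) = 0.16, and the plan's target difference is 0.25. That is fair, and it makes this a modest point.

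**Conclusion.** The contradiction is literal, appears in the definitions of both the primary and the secondary outcome, and must be reconciled. Which account of the surgery is right is not for this review to say.

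The statistical consequence is conditional. It arises only if the sequence in Sections 10.1 and 10.2 is followed, only for nodes outside the standard field, and only because no node set is defined. Its likely net direction is a small upward bias in 89Zr sensitivity and in the advantage over FDG. The size is at most about 0.9 to 2.5 points under an unsourced 2 to 6 out-of-field metastases, sensitivity 0.70 for both tests and 0.3 discordance, and less where fluorescence also prompts removal. Benign tracer-positive nodes from outside the field work against 89Zr through specificity. The documents do not show that the bias will occur, and the power figures in Section 12 are unaffected.

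**What to change.** 1. Reconcile Section 2.4 and the synopsis with Sections 10.1 and 10.2.
2. State in Section 12 that the primary node set is all nodes within the standard-of-care dissection field, **recorded before the 89Zr PET is read**, whether or not they are tracer-positive. A field recorded merely before surgery is not enough: the scan may be done up to the day before surgery and is read preoperatively, so the field could already reflect it.
3. Flag on the CRF any node excised from outside that field. Report these nodes separately, outside the sensitivity, specificity and NPV denominators for both tests. The criterion must be location, not the reason for removal: under the Section 10.1 wording, dropping every node removed on a signal would discard true positives inside the field.

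With this node set the excess computed above is zero whichever account of the surgery is kept. The cost is wording, one CRF flag per node, and possibly a few nodes leaving the primary denominator.
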